# Table 8: Stopping Guidelines for DLTs

#### 8.6 Analyses

Study populations and evaluation criteria are noted in Section 8.2. Adverse events will be summarized by frequency and magnitude of event. Incidence of DLTs will be monitored against the safety bounds above. The bounds are non-binding, and provide a guideline that may result in study modification or closure. Participants in cohorts 1 and 2 will be assessed for clinical response and will be classified by disease control by week 12 and at final assessement. DCR will be estimated along with a 95% confidence interval around the point estimate.

Immune response will be measured based upon the methods in Section 7.9. The criteria for defining immune responses have been reported for ELIspot assays (34). The circulating CD4+ T cell response rate to 6MHP peptides in participants treated with 6MHP vaccine plus ipilimumab will be assessed at each time noted in the study calendar. Maximum response over all time periods will be used to estimate the overall CD4+ T cell response. Other measures assessed over time in the blood include epitope-spreading for circulating CD8+ T cells reactive to a panel of defined melanoma antigens, and production of serum IgG reactive to 6MHP. Assessments in the tumor microenvironment include assessment for of CD8+ and/or CD4+FoxP3neg T cells into melanoma. Each participants experiencing an event (immune response, IgG antibody response to 6MHP, presence of CD8+ T cell infiltrates into the tumor (a subset), etc) will be estimated along with 95% confidence intervals. Repeated measure models will be explored to estimate changes over time in interval measurements in the blood and tissue.

Additionally, for cohort 3 only, estimates of immune response within the cohort will be estimated. We expect accrual of at least 15 eligible participants to cohort 3. At study conclusion, if 12/15 (80%) eligible participants satisfy the definition of immune response in cohort 3 then a 90%CI for immune response rate of 80% is (56%, 94%) which would support that immune response rate has improved in that cohort specifically.

PFS, DFS (within appropriate cohorts) and OS distributions will be estimated by the product limit method of Kaplan and Meier. Other summary measures for PFS, DFS and OS will include estimates and 95% CIs for median and 1-year estimates of PFS, DFS and OS to assess relative to published data. Clinical response by irRC criteria will be tabulated and cross classified by DCR. We acknowledge that participants who progress by RECIST criteria and then go onto other therapies may result in an underestimate of response by irRC criteria. However, if deemed appropriate some of these participants may be followed for a longer period before start of other treatment given that they received immune therapy and their response by irRC may be captured. Exploratory proportional hazard models will be used to obtain preliminary estimates of potential associations with T cell and antibody responses to melanoma antigens and survival.

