# Exploratory:

Induction of antibody responses: To estimate the production of serum IgG reactive to 6MHP in patients treated with 6MHP vaccines plus ipilimumab.

Clinical outcome (for cohorts 2 and 3): To obtain preliminary data on risk of recurrence and time to recurrence after resection of tumor to no evidence of disease and administration of the combination of 6MHP vaccine plus ipilimumab.

Associations of immune response and clinical outcome. To obtain preliminary estimates of the associations between T cell and antibody responses to melanoma antigens and survival and with disease control.

Clinical outcome (for cohort 1 only): To obtain preliminary estimates of clinical outcomes, including overall survival, progression-free survival, and clinical response by RECIST 1.1, following administration of the combination of 6MHP vaccine plus ipilimumab.

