# Clinical outcome

- For cohort 1: To obtain preliminary estimates of clinical outcomes including overall survival, progression-free survival, and clinical response by irRC criteria following administration of the combination of 6MHP vaccine plus ipilimumab.
- For cohorts 2 and 3: To obtain preliminary data on risk of recurrence and time to recurrence after resection of tumor to no evidence of disease and administration of the combination of 6MHP vaccine plus ipilimumab.

Associations of immune response and clinical outcome

• To obtain preliminary estimates of the associations between T cell and antibody responses to melanoma antigens and survival and with disease control.

T cell infiltration of the tumor microenvironment

• To determine whether the combination of 6MHP vaccine plus ipilimumab increases infiltration of CD8+ and/or CD4+FoxP3neg T cells into melanoma metastases in at least 50% of patients with tumor evaluable pre- and post-treatment.

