The lesions to be biopsied must be specified at study enrollment and not included as target lesions for RECIST calculations. There must be measurable disease in addition to the lesion(s) to be biopsied for cohort 1.

Up to 15 participants whose metastases are not available for biopsy may be enrolled in the first stage of enrollment, and up to 17 participants whose metastases are not available for biopsy may be enrolled in the second stage of enrollment.

- 3.1.4 Participants who have had brain metastases will be eligible if all of the following are true:
  - 3.1.4.1 Each brain metastasis must have been treated by surgical removal, stereotactic radiosurgery or managed to complete resolution with immunotherapy. Patients with brain lesions managed by immunotherapy without excision or radiosurgery are included provided that the brain metastases have completely resolved after systemic therapy and there are no neurologic symptoms or need for systemic therapy to control CNS-disease related symptoms.
  - 3.1.4.2 There has been no evident growth of any brain metastasis since the most recent treatment. If a patient has been managed by immunotherapy alone, the prior lesions must be completely resolved.
  - 3.1.4.3 No brain metastasis is > 2 cm in diameter at the time of registration
  - 3.1.4.4 The most recent surgical resections or gamma-knife therapy for malignant melanoma must have been completed ≥ 1 week prior to registration.
- 3.1.5 ECOG performance status of 0 or 1 (Appendix 3) (55)
- 3.1.6 Ability and willingness to give informed consent
- 3.1.7 Laboratory parameters as follows:
  - $3.1.7.1 \; ANC \geq 1000/mm^3$
  - 3.1.7.2 Platelets  $\geq$  100,000/mm^3
  - $3.1.7.3 \text{ Hgb} \ge 9 \text{ g/dL}$
  - 3.1.7.4 HgB-A1C ≤ 7.5%
  - 3.1.7.5 AST and ALT  $\leq$  2.5 x upper limits of normal (ULN)
  - 3.1.7.6 Bilirubin ≤ 1.5 x ULN (except in patients with Gilbert's disease, where bilirubin to 4x ULN is allowed).
  - 3.1.7.7 Alkaline phosphatase ≤ 2.5 x ULN
  - 3.1.7.8 Creatinine  $\leq 1.5$  x ULN
- 3.1.8 Age 18 years or older at registration.
- 3.1.9 Participants must have at least two intact (undissected) axillary and/or inguinal lymph node basins

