# (Cohort 1)

Disease control as assessed by the RECIST 1.1 (CR, PR, SD at 12 weeks) criteria.

Clinical response by irRC criteria.

Progression-free survival (PFS), defined as the time from the date of start of treatment to the date of progression or death from any cause, whichever occurs first. A participant who dies without a reported progression will be considered an event on the date of death. Participants who have neither progressed nor died will be censored on the date of last evaluable tumor assessment.

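### Section 8.6 classifies cohorts 1 and 2 by disease control and estimates a DCR with no cohort named, whereas Section 8.2.3 lists disease control under cohort 1

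*Combined protocol and SAP*

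**What the plan says.** Section 8.6 opens with a pointer: "Study populations and evaluation criteria are noted in Section 8.2". It then states that "Participants in cohorts 1 and 2 will be assessed for clinical response and will be classified by disease control by week 12", adds final assessment as a second time point, and continues: "DCR will be estimated along with a 95% confidence interval around the point estimate". That sentence names neither a cohort nor a denominator. Later in 8.6, irRC response is to be cross-tabulated against DCR.

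Section 8.2.3 divides the clinical measures by cohort. OS applies to everyone. Under the cohort 1 heading stand "Disease control as assessed by the RECIST 1.1 (CR, PR, SD at 12 weeks) criteria", irRC response and progression-free survival. Under the heading for cohorts 2 and 3 stands DFS alone.

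Sections 1.8 and 8.1 assign DCR to the advanced setting and recurrence to the neoadjuvant and adjuvant settings. Among the exploratory objectives in Section 2.3 is "For cohort 1: To obtain preliminary estimates of clinical outcomes including overall survival, progression-free survival, and clinical response by irRC criteria"; cohorts 2 and 3 get recurrence outcomes. The synopsis likewise restricts its clinical response objective to cohort 1. One further objective, in both places, carries no cohort limit: "To obtain preliminary estimates of the associations between T cell and antibody responses to melanoma antigens and survival and with disease control".

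**The concern.** Section 8.6 brings cohort 2 into a classification that 8.2.3 lists only for cohort 1, and then reports a rate without saying whose rate it is. Someone programming the analysis would have to choose the population.

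The choice matters because of what happens to cohort 2. Section 6.10 has these participants undergo surgery to become free of disease on day 22. The study calendar has no scan between screening and day 57. At the first post-baseline scan, the absence of disease in a resected participant reflects the operation at least as much as the drugs. The text available to us gives no rule for scoring such a participant as controlled, not controlled or not evaluable. A DCR that included cohort 2 would not measure what 1.8 and 8.1 say the trial should inform, namely disease control in advanced disease. The irRC-by-DCR table uses the same variable.

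**Working it through.** The plan states no DCR target, sample size or power, so there is no figure to reproduce. The check compares the passages and then sizes the ambiguity.

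**1. Which cohort has which measure**

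| Place | Disease control or DCR | Clinical response | Cohort 2 outcome |
|---|---|---|---|
| 8.6 | Classification: cohorts 1 and 2. DCR: no cohort named | Cohorts 1 and 2 | Not separated for DCR |
| 8.2.3 | Cohort 1 | Cohort 1 (irRC) | DFS, OS |
| 1.8 and 8.1 | Advanced setting | – | Recurrence |
| Synopsis and 2.3 | Association objective only, no cohort limit | Cohort 1 | Recurrence |

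The objectives therefore support a cohort 1 restriction directly for clinical response and only indirectly for disease control. The DCR point rests on 8.2.3, 1.8 and 8.1.

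**2. Timing in cohort 2**

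Surgery is on day 22 (6.10) and the first post-baseline scan is on day 57 (Appendix 1). The gap is 57 − 22 = 35 days. Day 57 is week (57 − 1)/7 = 8, and day 85 is week (85 − 1)/7 = 12.

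**3. Share of cohort 2 if the cohorts were pooled**

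Inputs from 8.3: cohort 1 at 1–3 per year, cohort 2 at 3–5 per year, cohort 3 at about 10, total about 16. Cohorts 1 and 2 together are thus about 16 − 10 = 6 per year. The share is c2/(c1 + c2):
- low: 3/(3 + 3) = 50%
- middle: 4/(4 + 2) = 67%
- high: 5/(5 + 1) = 83%

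**4. Size of cohort 1**

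Enrolling 27 at 16 per year takes 27/16 = 1.69 years, in line with the stated completion in under two years. Cohort 1 is then 1 × 1.69 = 1.7 to 3 × 1.69 = 5.1, or about 2–5 participants. Exact (Clopper-Pearson) 95% intervals: 1/2 gives 1.3–98.7%, 1/5 gives 0.5–71.6%, 2/5 gives 5.3–85.3%.

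**5. Illustration of what the denominator does**

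The counts and outcomes here are assumed. Section 8.6 expects at least 15 of the 24 eligible participants in cohort 3, which leaves at most 24 − 15 = 9. At the middle rates that splits as 3 in cohort 1 and 6 in cohort 2. Suppose one cohort 1 participant has disease control:
- cohort 1 alone: 1/3 = 33% (0.8–90.6%)
- pooled, resected participants scored as not controlled: 1/9 = 11% (0.3–48.2%)
- pooled, resected participants scored as controlled: (1 + 6)/9 = 7/9 = 78% (40.0–97.2%)

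The cohort 1 data are identical in all three lines.

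**6. The 12-week wording (secondary)**

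Section 8.2.3 requires stable disease at 12 weeks; 8.6 classifies by week 12. The Table 7 footnote makes day-85 scans conditional on need, and the calendar footnote ties them to verifying objective responses seen on day 57. A participant with stable disease on day 57 and no day-85 scan can be placed under the 8.6 wording. Under the 8.2.3 wording, scheduled imaging may not show their status at week 12.

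**The case against.** The best defence is that 8.6 begins by sending populations and criteria to 8.2, where the only disease control criterion stands under cohort 1, and that 8.4 stratifies participants by cohort. On that reading DCR already means cohort 1, and so does the irRC table, because irRC response is itself a cohort 1 measure. This has force for the DCR sentence and the table. It does not remove the explicit naming of cohort 2 in the sentence just before. The 8.2.3 lead-in, which covers all treated participants, does not help either: it refers to the measures that follow, and these are then split by cohort.

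Several stronger readings are tempting, and the documents do not support them.
- **That the cohorts are pooled.** Section 8.6 does not say so. The 50–83% share and the pooled rates are conditional.
- **That the objectives confine disease control to cohort 1.** The only objective that names disease control has no cohort limit.
- **That cohort 2 has no measurable disease.** Section 3.1.3 says "There must be measurable disease in addition to the lesion(s) to be biopsied for cohort 1", but 7.7 mentions measurable disease in biopsied participants without a cohort limit. The argument here rests on the day-22 resection instead.
- **That no scoring rule exists for resected participants.** None appears in the visible text, but the cohort 2 schema figure is not shown.
- **That a planned association analysis is compromised.** Section 8.6 specifies models for survival only. What is missing is a statement of the cohort for any disease control association.

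**Conclusion.** The inconsistency is real and in current text: 8.6 extends disease control classification to cohort 2 and leaves the DCR cohort unnamed, while 8.2.3, 1.8 and 8.1 place disease control in the advanced cohort. Applied to cohort 2, the measure would largely record surgical clearance.

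If the cohorts were pooled, cohort 2 would supply about 50–83% of the denominator, and the rate would depend mainly on how resected participants are scored. These figures assume the projected accrual rates; the 11% and 78% in the illustration also assume the counts and outcomes. With cohort 1 at about 2–5 participants, the correctly restricted DCR will have a very wide interval and can only be descriptive.

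Severity is minor. A reader might infer that the trial's conclusions are at risk. They are not: DCR is exploratory, and neither the sample size, the immune response criterion nor the safety bounds use it. The 12-week wording is a smaller, separate matter.

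**What to change.** In 8.6:
- limit the DCR estimate to cohort 1, both at week 12 and at final assessment, consistent with 8.2.3;
- state that the irRC-by-DCR table uses cohort 1;
- report cohort 2 by DFS and OS, and if any response assessment is kept for cohort 2, report it separately and outside the DCR;
- name the cohort for any analysis associating immune response with disease control.

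In 8.2.3 and 8.6, use one wording for the 12-week time point, reconcile it with the imaging calendar, and say how a participant with stable disease on day 57 and no day-85 scan is classified.

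The cost is a few sentences. No scans, participants or data items are added. Settling the wording before analysis prevents the denominator from being chosen after the results are seen.

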#### 8.2.2 Immunogenicity

All eligible participants receiving any protocol treatment will be evaluated for the following immune response parameters.

i. Primary:

Circulating CD4+ T cell response to 6MHP peptides where the primary endpoint is the proportion of participants with at least two consecutive 10-fold over baseline responses to the pool of 6MHP peptides.

CD4+ T cell response to 6MHP peptides in the SIN.

ii. Secondary:

Evaluated in the blood and in the SIN

Induction of epitope-spreading for CD8+ T cells reactive to a panel of defined melanoma antigens.

*Evaluated in the tumor microenvironment* (In the subset of participants for which tumor biopsies are obtained pre- and post- treatment) T cell infiltration of CD8+ and/or CD4+FoxP3neg T cells.

iii. Exploratory:

Induction of antibody responses

IgG antibody responses to 6MHP peptides.

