#### 8.2.3 Clinical efficacy

All participants receiving any protocol treatment will be evaluated for clinical response to treatment as defined by the following measures.

- i. Exploratory:
  - Overall survival (OS), defined as the time from the date of start of treatment to the date of death from any cause. Participants who do not experience an event (death) will be censored on the date of last follow-up/contact.

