# 8.4 Cohort and post entry classification

At study entery participants will be stratified by cohort. In addition. Participants will be monitored for post entry classification by whether or not biopsies are obtained at baseline and one week after the third vaccine; (yes/no). Target sample size for participants for whom biopsies are obtained is set at a minimum of 14 eligible participants. If increased infiltration of CD8+ T cell response from day 1 compared to day 22 tumor is observed in 10/14 participants then the lower limit of a one-sided 90% confidence interval exceeds 50% and would be considered to support further study of the treatment regimen. Similar criteria apply for CD4+FoxP3neg T cells response.

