f History & physical, comprehensive chemistry, and CBC with differential scheduled for Day 1 are not required if prestudy assessments were within 10 calendar days of day 1. However, hair and eye color assessment and assessment of skin for vitiligo should be performed if theses assessments were not completed as part of the pre-study visit. gFor patients who have tumor accessible to biopsy, biopsies will be completed 1) during screening or, once enrolled, prior to treatment on Day 1, and 2) at day 22, for subjects who have melanoma available for biopsy. Additional optional biopsies may be performed for research purposes during the study or during follow-up if participants are removed from the study or experience progression. If surgical resection or biopsies are completed for clinical care, the tumor tissue may be collected for study related analyses.

h Tumor imaging at day 85 should be performed only when clinically needed to verify objective clinical responses at day 57.

If scans were completed at day 85, the scans do not have to be repeated at this visit.

 Scans do not need to be repeated for the protocol if they have been performed recently (typically within 3 months).

kBlood for HLA typing is included in the research bloods.

Required only for subjects with brain metastases.

mFollow-up visits in the initial follow-up phase will occur as follows: FUv1: 42 days from the last dose of 6MHP; FUv2 = 24 weeks from the first dose of 6MHP; FUv3 = 27 weeks from the first dose of 6MHP; FUv4 = 1 year from the first dose of 6MHP; FUv5 = 2 years from the first dose of 6MHP.

nOnly information about anticancer therapy will be collected

T Classification	Thickness	Ulceration Status						
τ.	< 1.0 mm	a: without ulceration or mitoses						
	S 1.0 mm	b: with ulceration or mitoses $\geq 1$						
Т2	1.01 2.0 mm	a: without ulceration						
12	1.01 – 2.0 mm	b: with ulceration						
Т2	2.01 4.0 mm	a: without ulceration						
15	2.01 – 4.0 mm	b: with ulceration						
Тл	> 1 0 mm	a: without ulceration						
14	24.01111	b: with ulceration						

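### The response-survival models in Section 8.6 have no landmark, time-dependent covariate or cohort term, so an ever-responder analysis from day 1 would be biased towards benefit

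*Combined protocol and SAP*

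**What the plan says.** The association is a stated exploratory objective in Section 2.3: "To obtain preliminary estimates of the associations between T cell and antibody responses to melanoma antigens and survival and with disease control". Section 8.6 gives the method in one sentence: "Exploratory proportional hazard models will be used to obtain preliminary estimates of potential associations with T cell and antibody responses to melanoma antigens" and survival. The parts that the model would use are defined elsewhere.

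- **Time origin (Section 8.2.3).** Overall survival (OS) is "defined as the time from the date of start of treatment to the date of death from any cause". PFS (cohort 1) and DFS (cohorts 2 and 3) have the same origin.
- **Population (Section 8.2.3).** "All participants receiving any protocol treatment will be evaluated for clinical response to treatment", which for OS means all three cohorts.
- **Response (Section 8.2.2).** The primary blood endpoint requires "at least two consecutive 10-fold over baseline responses to the pool of 6MHP peptides".
- **Window (Section 8.6).** "Maximum response over all time periods will be used to estimate the overall" CD4+ T cell response. No cut-off is given.
- **Draws (Appendix 1).** Research blood is taken on days 1, 8, 15, 22, 43, 64, 85 and 92 and at weeks 18, 24, 27, 52 and 104. The last visit is "FUv5 = 2 years from the first dose of 6MHP".
- **Cohort (Section 8.4).** "At study entery participants will be stratified by cohort". Section 8.6 ties the PFS and DFS curves to their cohorts. It does not say whether cohort enters the hazards models.

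**The concern.** The only blood response status that the plan defines is an ever-responder status, and it becomes known some time after day 1. A participant must live, and stay in sampling, long enough to be classed as a responder. Anyone who dies first is a non-responder by construction, and the weeks that responders had to survive before confirmation are credited to the responder group. This is immortal-time bias. It favours responders, and more participants would not remove it.

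The protocol offers a second route. Under Sections 6.1 and 9.4.2 a participant leaves treatment follow-up on starting another therapy and is then followed yearly for progression and survival. Scheduled sampling can therefore end near progression while the OS clock runs on. Early progressors lose the chance to convert and also tend to die sooner.

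OS covers participants from resected stage IIA to unresectable stage IV. If response rates differ between cohorts, an OS model without a cohort term mixes prognosis with response.

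Section 1.5 uses the same kind of association in E1602 (p = 0.005; multivariate hazard ratio 0.5) to support the clinical relevance of the immune response. An artefactual ratio of similar size here could look like replication. Nothing in this point says that the E1602 result was biased.

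**Working it through.** **The plan's own figure.** None is stated for these models: no number of events, power, alpha or hazard ratio. The only powered figure is the immunogenicity rule in Section 8.3 (at least 18/24; 55% versus 80%). It reproduces (exact power 0.811, one-sided alpha 0.036) and does not bear on this point.

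**Step 1: the mechanism by hand, with no true effect.** Inputs:
- Median OS 10.0 months (ipilimumab-alone arm quoted in Section 1.6) = 10.0 × 52.18/12 = 43.5 weeks, so λ = ln 2/43.5 = 0.01594 per week for everyone.
- Share of potential responders p = 0.55 (the null rate in Section 8.3).
- Assumed: all responses confirmed at t = 12 weeks, follow-up 104 weeks.

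Let a = exp(−12λ) = 0.8259 and b = exp(−104λ) = 0.1906.

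- Ever-responders: deaths p(a − b) = 0.349; person-weeks p[12a + (a − b)/λ] = 27.37; rate 0.01277.
- Others: deaths (1 − p)(1 − b) + p(1 − a) = 0.364 + 0.096 = 0.460; person-weeks (1 − p)(1 − b)/λ + p[(1 − a)/λ − 12a] = 22.85 + 0.56 = 23.41; rate 0.01965.
- Rate ratio = 0.01277/0.01965 = 0.65, although the true ratio is 1.

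Counted from week 12 among those alive, both groups have rate λ and the ratio is 1. The same formula with other inputs gives:

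| Median OS | p | Confirmed at week | Rate ratio |
|---|---|---|---|
| 10.0 months | 0.55 | 6 | 0.79 |
| 10.0 months | 0.80 | 12 | 0.46 |
| 6 years (assumed) | 0.55 | 12 | 0.76 |
| 6 years (assumed) | 0.80 | 12 | 0.58 |
| 6 years (assumed) | 0.80 | 27 | 0.35 |

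These are corner cases, because every confirmation falls on one date. The 0.46 also gives everyone advanced-disease survival.

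**Step 2: simulation for the trial's mix, with no true effect.** Cohorts of 3/7/17, in line with the accrual rates in Section 8.3. Median OS is 10 months in cohort 1; 3 to 5 years (cohort 2) and 6 to 10 years (cohort 3) are assumed. Response rates are 55% or 80% throughout, or differ by cohort using the rates in Section 1.5. Survival is exponential, with censoring at 2 to 4 years. The Cox model has ever-responder status fixed from day 1 and cohorts pooled.

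| Confirmation times (assumed) | Large-sample HR | False benefit at N = 27 (nominal 2.5%) |
|---|---|---|
| All by week 12 | 0.77–0.97 | 2.4%–8.3% |
| Spread to week 27 | 0.58–0.85 | 3.1%–14.6% |
| Spread to week 104 | 0.38–0.65 | 4.9%–34.7% |

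A further null simulation gave about 0.6 to 0.9 for confirmation by week 12, hence the overall range of roughly 0.6 to 0.97. Stratifying by cohort alone does not cure the bias (0.42–0.92).

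**Step 3: sampling that stops at progression.** Models stratified by cohort; median PFS or DFS assumed at 13–22, 104–156 and 156–260 weeks in cohorts 1, 2 and 3. With confirmation by week 12, the OS ratio is 0.90–0.99 if sampling ends only at death and 0.65–0.86 if every progression ends it. The latter is an upper case.

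**Step 4: pooling alone, with response known at time 0.**
- Equal response rates across cohorts: 0.99–1.03.
- Cohort 1 responds less (40% versus 52%): 0.87–0.92.
- Cohort 1 responds more (57% versus 48%): 1.07–1.11.

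Section 1.5 reports 40% and 57% in advanced disease and 48% or 52% in resected disease, so the documents do not fix the direction.

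**Step 5: after the change, in the Step 2 scenarios.** The week-13 landmark stratified by cohort gives 0.95–1.02 in large samples. At N = 27 its median ratio ranges from 0.74 to 1.41, because only about 8 to 11 deaths are expected in the whole study. Time-dependent response at N = 27 gives medians of 0.88–1.02 and false benefit in 0.4%–5.1% of trials.

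**The case against.** A reader might infer that the plan enters response as a baseline covariate, pools the cohorts, and will therefore show a benefit where none exists. The documents do not support that reading. Section 8.6 is silent on how response enters and on whether cohort is a term. Participants are stratified by cohort at entry, and PFS and DFS belong to particular cohorts, so pooling is a live question mainly for OS. The maximum over time is named for estimating the response rate, not as the survival covariate.

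The size is also open to challenge. There are seven post-baseline draws by day 92, and two consecutive rises could be confirmed by day 15. With 55% responders and early confirmation the ratio is about 0.9 in the Step 2 setting, with false benefit near the nominal rate. Constant hazards from day 1 probably overstate early deaths in a mostly disease-free group with ECOG status 0 or 1. The node response is taken once, on day 22, and carries little immortal time. The analysis is exploratory, has few deaths and cannot alter the 18/24 decision.

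All of this stands, and it limits the claim to a bias that the plan does not prevent. It does not remove the direction of the timing bias, which holds for any ever-responder analysis from day 1. Nor does entry stratification in a non-randomised study put a cohort term into a model.

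**Conclusion.** The point holds as a gap with a predictable consequence. Combining the plan's own response definition with its own time origin, without a timing device, biases the association towards benefit. With no true effect, the hazard ratio is roughly 0.6 to 0.97 if responses are confirmed by week 12, and lower if later conversions count. These are scenarios resting on assumed response rates, confirmation times and survival in cohorts 2 and 3; they do not forecast the trial's result. Pooling for OS adds confounding that could go either way. The consequence is confined to an exploratory objective, but the remedy is cheap and uses a draw already scheduled.

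**What to change.** Add to Section 8.6: associations of blood T cell and antibody responses with OS, PFS and DFS will classify response from samples up to a week-13 (day 92) landmark, in participants event-free at that time, with time counted from the landmark, and/or will enter response as a time-dependent covariate; OS models will be stratified by cohort or reported by cohort; results are descriptive.

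Day 92 follows the sixth vaccine (day 85) and is already a research draw, so no visit, sample or participant is added. The landmark drops events before week 13 and treats responses first seen later as non-responses. The time-dependent model keeps all events. With about 27 participants either estimate will be imprecise, and three strata with perhaps 3 participants in cohort 1 leave little information. Because sampling can stop when another therapy starts, the report should also give the number who left sampling before week 13.
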